9.2 Parameters

All parameters through which the study objectives will be carried out, will be listed. Exact computations are declared in [Section 11.2](#).

Primary and secondary efficacy assessments will be performed centrally by independent readers who will be blinded with regard to patient identity and all clinical information of a patient.

Independent readers and on-site radiologists will assess focal liver lesions on images from unenhanced, combined and mangoral-enhanced MRI described in detail in Section 6.2.1 of the protocol.

9.2.1 Visualization of lesions

In every patient, up to 15 lesions will be assessed by each MRI method: unenhanced MRI, mangoral-enhanced MRI and CMRI (on-site and independent off-site readers' assessments).

At the time of efficacy reads, the three independent readers will identify the location of the detected lesions in liver segments. A fourth reader who is not involved in efficacy reads will track and match the detected lesions on unenhanced, mangoral-enhanced and combined (unenhanced plus mangoral-enhanced MRI)

to confirm lesion numbering and lesion location across the modalities. Lesion tracking will also confirm lesions that are identified on pre-mangoral, post-mangoral and combined MRI images for inclusion in the analysis of the co-primary variables.

9.2.2 Primary Efficacy Parameter

The primary efficacy endpoint is the visualization of detected focal liver lesions in combined MRI (CMRI, mangoral-enhanced MRI plus unenhanced MRI) as compared to unenhanced MRI.

The visualization will be assessed using two co-primary variables:

- lesion border delineation (BD)
- lesion contrast compared to the liver background (LC).

Both parameters will be determined for each lesion (up to 15 lesions per patient) and by each of the 3 independent readers by qualitative assessment on 4-point scales with categories 'poor' (1), 'partial / moderate' (2), 'good' (3) and 'excellent' (4) lesion border delineation/lesion contrast (defined in the Section 6.2.3.1 of the study protocol). Based on the scores on the 4-point scales, two sum scores will be calculated for each patient and separately for each MRI method: a lesion border delineation sum score and a lesion contrast sum score. Both scores will be weighted by the number of lesions per patient.

For primary efficacy endpoint analysis, only lesions that are seen on both pre- and post-contrast (Part I and Part II) will be considered and results of individual readers will be reported separately. The matcher will match lesions for unenhanced, enhanced and combined MRI. It is possible, that lesions are not seen on an unenhanced MRI scan, but become visible on the combined MRI and/or enhanced MRI scan. Since the primary endpoint refers to the visualization of the lesion, in this event, these lesions will not be considered for the primary efficacy analysis.

9.2.3 Secondary Efficacy Parameters

The secondary efficacy variables will be based on the evaluations by independent readers (off-site readers' assessment) and selected endpoints (number of lesions per MRI method, change in patients' management and confidence in lesion detection and localization and change in patients' management) also by the on-site radiologist (on-site readers' assessment) as specified in [Table 1](#). The secondary efficacy endpoints assessed off-site will be evaluated using the same number of lesions as the primary endpoint, if not specified otherwise.

9.2.3.1 Number of lesions detected by each MRI method and proportions of patients

Number of lesions detected by each MRI method (unenhanced MRI, mangoral-enhanced MRI and CMRI) per patient will be presented using descriptive statistics.

In addition, the following proportions of patients will be calculated for assessments performed by independent off-site readers:

- The number of patients having at least one lesion identified on post-mangoral images that was not identified on pre-mangoral images.
- The number of patients having at least one malignant lesion identified on post-mangoral images that was not identified on pre-mangoral images based on patients with at least one malignant lesion at baseline. For patients with malignant lesions at baseline any new lesions identified are also assumed to be malignant.
- The number of patients who had improvement in at least one co-primary variable for at least one lesion on post-mangoral images compared to pre-mangoral images.

9.2.3.2 Visualization in mangoral-enhanced MRI vs. unenhanced MRI

Visualization of focal liver lesions in mangoral-enhanced MRI as compared to unenhanced MRI will be assessed in the same way as for the primary efficacy endpoint (by the off-site readers only).

9.2.3.3 Confidence in lesion detection and localization

Confidence in lesion detection is defined in [Section 11.2.3](#) and will be assessed separately in unenhanced MRI, mangoral-enhanced MRI and CMRI (3-point scale, on-site and independent off-site readers' assessments of up to 15 lesions per patient).

Confidence in lesion localization is defined in [Section 11.2.4](#) and will be assessed separately in unenhanced MRI, mangoral-enhanced MRI and CMRI (3-point scale, independent on-site and off-site readers' assessments of up to 15 lesions per patient).

The lesions will be listed in ordinal sequence from the smallest to the largest with specification of the liver segment in which they have been identified. For assessments provided by on-site readers, all lesions detected per MRI method (regardless if they are matched compared to unenhanced MRI) will be included in descriptive statistics.

9.2.3.4 Lesion dimensions

Lesion dimension measurements (diameter measured in mm) will be done by each of the 3 independent readers on mangoral-enhanced MRI and unenhanced MRI images for all lesions. The longest diameter of the largest and of the smallest visualized lesions, respectively, will be summarized.

9.2.3.5 Quantitative assessments

Quantitative assessments are specified in [Section 11.2.5](#) and will be performed for up to 5 detected lesions (independent off-site readers' assessment). These lesions will be the same for pre- and post-contrast assessments:

- liver signal intensity (SI) enhancement (%);
- liver-to-lesion contrast (LLC);
- signal-to-noise ratio (SNR);
- contrast-to-noise ratio (CNR).

9.2.3.6 Change in patients' management

Change(s) in patients' management based on diagnostic performance of CMRI or mangoral-enhanced MRI versus unenhanced MRI (on-site and independent off-site readers' assessments):

- Any changes in patient management based on MRI findings (yes / no);
- Next steps in patient management based on MRI findings (i.e. chemotherapy, surgery, local ablation procedure, combination therapy).

A patient can have more than one recommended management per MRI method, for this reason all results will be included in the listings and the tables.

9.2.4 Safety Parameters

This section defines the general principles for the analysis of categorical and continuous parameters, unless specified otherwise. In general, the analysis of all parameters will be done by visit/time point and treatment group and overall.

Categorical parameters will be descriptively summarized per visit/time point and overall post-baseline. For an overall post-baseline analysis, the worst value during the on-treatment period, including unscheduled visits, will be derived. If applicable, the number of not exact values will be displayed in the respective table. Continuous parameters will be descriptively summarized. Changes from baseline will be presented for all post-baseline visits/time points. Baseline values are defined as described in [Section 11.2.1](#).

Where applicable, continuous laboratory parameters will be classified as *low*, *normal*, or *high* based on reference (normal) ranges as provided by the central laboratories.

A listing of patients with values outside the reference ranges will be provided. All parameter values will be presented in a patient data listing including respective flagging with respect to reference ranges.

Unscheduled measurements of parameters will be presented in the patient data listing. In general, unscheduled measurements will not be included in the analysis.

9.2.4.1 Vital signs

Vital signs will be measured at baseline (within 3 hours prior to contrast administration) and after contrast administration at 6 (± 1) hours, 24 (± 4) hours, 48 (± 4) and 5 (± 2) days post-dose:

- Systolic blood pressure [mmHg];
- Diastolic blood pressure [mmHg];
- Pulse rate [bpm];
- Respiratory rate [breaths per minute];
- Body temperature [$^{\circ}\text{C}$].

The investigator will report any worsening from baseline in vital signs as AE (see Section 6.3.7 of the protocol).

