### **6.3.1 Vital signs**

Vital signs will be measured at baseline within 3 hours prior to contrast administration, and after contrast administration at 6 ( $\pm$  1) hours, 24 ( $\pm$  4) hours, 48 ( $\pm$  4), and 5 ( $\pm$  2) days post-dose:

- Systolic blood pressure (mmHg)
- Diastolic blood pressure (mmHg)
- Pulse rate (bpm)
- Respiratory rate (breaths per minute)
- Body temperature ( $^{\circ}$ C)

Patients must be sitting, and measurements must be started after at least 4 minutes of rest. The investigator will evaluate any worsening in vital signs. Any new or worsening events (irrespective of clinical significance) observed after mangoral administration compared to previous pre-dose assessments must be reported as an AE.

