### **6.3.4 Electrocardiogram (ECG)**

A 12-lead ECG will be performed after 5 minutes supine rest at baseline (within 3 hours prior to contrast administration) and after administration of mangoral at 6 ( $\pm$  1) and 24 ( $\pm$  4) hours post-dose.

Standard ECG parameters will be recorded and assessed (including corrected QT interval, RR interval, PR interval, and QRS interval).

The investigator will record on the eCRF whether the results are normal, abnormal (not clinically significant or clinically significant). If recorded as abnormal and clinically significant, the abnormality must be reported in the eCRF as an AE (Section [6.3.7](#)).

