#### **6.3.7.1      Definition of adverse events**

An AE is any untoward medical occurrence in a patient or clinical investigation subject administered a pharmaceutical product and does not necessarily have a causal relationship with this treatment. An AE can therefore be any unfavourable and unintended sign (including abnormal laboratory finding), symptom, or disease temporally associated with the use of an IMP, whether or not related to the IMP.

Symptoms or clinically significant laboratory or instrumental (e.g. electrocardiographic) abnormalities of a pre-existing condition, such as cancer or other diseases, should not be considered an AE. However, the occurrence of new symptoms, or laboratory, or instrumental abnormalities, and the worsening of pre-existing symptoms, are considered AEs.

Laboratory values outside the normal laboratory-specific reference ranges that make intervention necessary and / or are considered clinically significant by the investigator must be reported as AEs. If the abnormal laboratory value is a sign of a disease, only this diagnosis should be reported as an AE.

An AE is considered an adverse drug reaction (ADR) if a causal relationship between a medicinal product and an AE is at least a reasonable possibility.

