### **7.2.4 Follow-up visit V4 (day 1)**

The following examinations will be carried out and / or recorded on the first day following the day of mangoral dosing and the mangoral-enhanced MRI (24 [ $\pm$  4] hours post-dose):

- Any changes in concomitant therapies (including medications taken only once and any non-prescription medicine)
- Vital signs at 24 hours post-dose (Section 6.3.1)
- Physical examination at 24 hours post-dose (Section 6.3.2)
- Neurological assessments at 24 hours post-dose (Section 6.3.3)
- ECG at 24 hours post-dose (Section 6.3.4)
- Blood sampling for clinical safety laboratory tests (haematology, biochemistry) at 24 hours post-dose (Section 6.3.5.2)
- Urine collection for urinalysis at 24 hours post-dose (Section 6.3.5.2)
- Blood sampling for determination of manganese concentration at 24 hours post-dose (Section 6.3.5.3)
- Adverse events (Section 6.3.7)

If Visit 4 is conducted as a remote visit, the reason for the change of the visit type shall be recorded in the medical records. As a minimum, information on possible adverse events and changes in concomitant medication must be collected.

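### Worsening of a vital sign is an AE without a definition of worsening, so the any-AE and probably the related-AE proportions will mainly reflect how sites apply the rule

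*SAP*

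**What the plan says.** SAP 9.2.4.1 has the rule in its short form: "The investigator will report any worsening from baseline in vital signs as AE". It then refers to protocol 6.3.7 and gives no threshold. Protocol 6.3.1 first says "The investigator will evaluate any worsening in vital signs" and then "Any new or worsening events (irrespective of clinical significance) observed after mangoral administration compared to previous pre-dose assessments must be reported as an AE". The statement that clinical significance does not matter is in the protocol only, not in the SAP sentence.

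Other assessments follow other rules:

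- **ECG (protocol 6.3.4):** "If recorded as abnormal and clinically significant, the abnormality must be reported in the eCRF as an AE".
- **Laboratory (protocol 6.3.7.1):** "Laboratory values outside the normal laboratory-specific reference ranges that make intervention necessary and / or are considered clinically significant by the investigator must be reported as" adverse events.
- **Physical examination and neurological assessment (protocol 6.3.2 and 6.3.3):** the same broad wording as for vital signs.

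Five signs are measured (systolic and diastolic pressure, pulse, respiratory rate, temperature), once within 3 hours before dosing and then at "6 (± 1) hours, 24 (± 4) hours, 48 (± 4) and 5 (± 2) days post-dose". Visits V4 and V5 may be remote outside the PK subgroup, and then "As a minimum, information on possible adverse events and changes in concomitant medication must be collected" (protocol 7.2.4; 7.2.5 is the same), so vital signs may be absent at 24 h and 48 h.

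SAP 13.8.1 tabulates all AEs, related AEs, SAEs, grade 3 or greater AEs, AEs by system organ class and preferred term, and post-dose preferred terms seen in at least 5% of dosed patients. The overview and the main frequency tables are split into pre-dose and post-dose. SAP 13.8.2 separately summarises vital signs and their changes from baseline.

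**The concern.** A single pre-dose reading is compared with up to 20 post-dose readings per patient. If worsening means any unfavourable difference, ordinary variation is enough to meet the rule, and the share of patients with an AE says little about mangoral. If sites use their own threshold instead, the share depends on a choice that is not written down and may differ among the roughly 60 sites.

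Four features of the plan add to this:

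- There is one treatment and no control arm (SAP 9.4), so no comparator carries the same noise.
- Under protocol 6.3.7.2 an AE counts as related unless a causal link can be excluded with certainty, and a missing relationship is counted as related (SAP 11.1.2). A chance change in pulse is hard to exclude on that standard.
- The vital-sign rule applies only after dosing, so it adds events to the post-dose column and none to the pre-dose column.
- The AE tables combine assessments held to different standards.

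**Working it through.** The documents give no expected AE rate, no within-patient variability and no threshold, so there is no planned figure to reproduce. The consequence of the rule can be calculated directly.

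**Inputs from the documents:** 5 signs; T = 4 post-dose times, or T = 2 if V4 and V5 are remote without vital signs; one scheduled baseline reading.

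**Assumptions:** no drug effect, exchangeable continuous readings within a patient, and one adverse direction per sign unless stated.

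**Literal rule, no threshold.** A sign shows no worsening only if baseline is the most favourable of the T + 1 readings, which has probability 1/(T + 1). For 5 independent signs, P(at least one AE) = 1 - (1/(T + 1))^5.

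- T = 4: 1 - (1/5)^5 = 99.97%
- T = 2: 1 - (1/3)^5 = 99.6%

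If all five signs move together they act as one: 1 - 1/5 = 80% (T = 4) or 1 - 1/3 = 67% (T = 2). No SD is needed for these four figures. In 80 patients, the number in SAP 9.1, independence would leave 80 × (1/5)^5 = 0.03 or 80 × (1/3)^5 = 0.33 patients without such an AE. Rounding readings to whole units (0.1 °C for temperature), with assumed within-patient SDs of 8, 5, 6, 1.5 and 0.2 in the order systolic, diastolic, pulse, respiration, temperature, gives 99.9% and 99.2%.

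**Unwritten threshold.** Suppose a site reports only changes above c within-patient SDs of a single reading. Simulation of 400,000 patients with Gaussian readings and 5 independent signs gives the share with at least one noise-only AE:

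| Threshold c | T = 4, one direction | T = 4, either direction | T = 2, one direction | T = 2, either direction |
|---|---|---|---|---|
| none | 99.97% | 100% | 99.6% | 100% |
| 1 SD | 97% | >99.9% | 90% | 99.8% |
| 2 SD | 70% | 93% | 51% | 79% |
| 3 SD | 24% | 44% | 15% | 28% |
| 4 SD | 4% | 8% | 2% | 4.5% |

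**Effect on the any-AE proportion.** Let p be the noise-only proportion and q the incidence of other AEs, assumed independent. The observed proportion is p + (1 - p)q.

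- p = 99.97%: q = 10% gives 99.97% and q = 30% gives 99.98%.
- p = 80%: the values are 82% and 86%.
- p = 67%: they are 70% and 77%.

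**Effect on the at-least-5% table.** One sign, one direction, T = 4: noise alone puts 21% of patients over a 2 SD threshold and 5.4% over a 3 SD threshold. Vital-sign terms could therefore reach the 5% cut-off without any drug effect.

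**The case against.** The strongest reply is that the rule was not meant numerically. The SAP sentence points to protocol 6.3.7, where an AE is an untoward occurrence or an unfavourable, unintended sign. Protocol 6.3.1 asks the investigator to evaluate worsening and attaches the reporting duty to events. On this reading a rise of 1 mmHg is not an AE. That stands as a plausible reading, and it is why the near-100% figure must stay conditional. It does not supply a threshold, and the protocol removes the filter that investigators would most naturally use.

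A reader might infer that virtually every patient will in fact be an AE patient. The documents do not support that: it needs a zero threshold at every site and largely independent signs.

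A reader might also infer that the AE data as a whole cannot discriminate. That goes too far. Preferred-term rows are counted per patient, so a blood-pressure AE leaves the nausea, diarrhoea or neurological rows unchanged. In the at-least-5% table noise adds rows and removes none. SAEs, grade 3 or greater AEs and the change-from-baseline summaries stay usable, and the IDSMB reviews all available safety data (protocol 7.3). In an uncontrolled trial the any-AE proportion could not by itself separate drug effect from background in any case.

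A third inference is that the vital-sign rule is a slip to be narrowed to clinically significant changes. The same wording for physical and neurological examinations suggests deliberate broad capture. Narrowing it is a debatable trade-off, needs a formal amendment (protocol 10.2), and part-way through could split the AE data between two definitions.

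**Conclusion.** The point holds in a limited form. Vital-sign worsening is an AE by rule, worsening is undefined, and the standard differs from that for ECG and laboratory values. Noise alone would give an AE to 99.6% to 99.97% of patients under the literal rule with independent signs, 67% to 80% if all signs move together, 15% to 44% at 3 SDs and 2% to 8% at 4 SDs. The zero-threshold figures rest on exchangeable readings. The threshold figures also assume Gaussian readings and independent signs, and the thresholds themselves are illustrative because the documents give none.

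That spread is the finding. The overall post-dose any-AE proportion, and probably the related-AE proportion, would depend more on how sites apply the rule than on mangoral. Vital-sign terms may also fill the at-least-5% table. The remaining safety summaries and all efficacy results are unaffected. It is a reporting weakness worth correcting at low cost, not a threat to the trial's main conclusion.

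**What to change.** Keep the capture rule for data already collected and change the presentation.

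1. **SAP 13.8.1:** present the any-AE, related-AE and at-least-5% summaries twice, once with all AEs and once excluding AEs that rest only on a vital-sign reading.
2. **Identification:** use a list of MedDRA preferred terms agreed before database lock. The documents do not provide for a clinical-significance rating of vital-sign findings, so the exclusion should not depend on one. A preferred term cannot by itself separate a bare reading from a symptomatic event, so the exclusion can optionally be limited to grade 1 events with no measure taken. Both fields are collected under protocol 6.3.7.2.
3. **Wording:** reconcile protocol 6.3.1, SAP 9.2.4.1 and protocol 6.3.7.1 on what counts as worsening.

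The cost is one extra set of AE tables and a preferred-term list to agree. No data are lost: the full AE tables remain, and SAP 13.8.2 still summarises and lists all vital-sign values.

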9.2.4.2 Physical examination

A physical examination will be performed at the following times: baseline (within 3 hours prior to contrast administration) and at 6 (± 1) hours, 24 (± 4) hours, 48 (± 4) hours and 5 (± 2) days post-dose. Any abnormalities must be specified in the eCRF and recorded as an AE (see Section 6.3.7 of the protocol).

9.2.4.3 Neurological assessments

Neurological assessments to monitor for any potential neurotoxic effects will be performed pre-dose during the baseline period and 24 (± 4) hours, 48 (± 4) hours and 5 (± 2) days hours after the administration of mangoral.

Results of the assessments will be recorded in the eCRF. All new (i.e. no pre-existing condition) abnormal findings observed after mangoral administration must be recorded and reported as AEs (see Section 6.3.7 of the protocol).

9.2.4.4 Electrocardiogram (ECG)

A 12-lead ECG will be performed after 5 minutes supine rest at baseline (within 3 hours prior to contrast administration) and after administration of mangoral at 6 (± 1) and 24 (± 4) hours post-dose.

ECG parameters will be recorded and assessed: overall interpretation, heart rate (beats/min), QT interval (msec), RR interval (msec), PR interval (msec), QRS duration (msec), QTcB interval (msec) and QTcF interval (msec).

The investigator will record on the eCRF whether the results are normal, abnormal (not clinically significant or clinically significant). If recorded as abnormal and clinically significant, the abnormality must be specified in the eCRF and if observed after administration of mangoral, the abnormality must also be recorded as an AE.

Note: As specified in Section 6.3.7 of the protocol, if electrocardiographic abnormalities observed in a pre-existing condition are preserved also after the administration of mangoral, these should not be considered as AEs. Only if abnormalities are worsening of pre-existing ones, they are considered as AEs.

9.2.4.5 Laboratory variables

Details of laboratory parameters are specified in Section 6.3.5 of the protocol. In summary, [Table 2](#) provides an overview of the screening laboratory tests and [Table 3](#) provides an overview of other laboratory parameters measured at baseline and post-dose visits.

The investigator has to document the clinical significance of abnormal laboratory values in the eCRF. If the clinically significant abnormal value is observed after administration of mangoral, the abnormality must also be recorded as an AE.

Table 2 Screening laboratory parameters

Child-Pugh: (local lab)	Serum bilirubin Serum albumin International normalized ratio (INR)	eGFR: (local lab)	Estimated Glomerular Filtration Rate (eGFR) Serum creatinine Serum albumin Serum urea nitrogen (SUN/BUN)
-----------------------------------	--	-----------------------------	---

Table 3 Clinical safety laboratory parameters (baseline and post-dose)

Hematology: (central lab)	Hemoglobin Hematocrit Erythrocytes Leukocytes Platelets Neutrophils Eosinophils, Basophils Lymphocytes Monocytes INR	Biochemistry: (central lab)	Alkaline phosphatase Aspartate aminotransferase (AST) Alanine aminotransferase (ALT) Gamma-glutamyl transferase (GGT) Creatinine Glucose Urea Total Bilirubin Albumin Sodium Potassium Calcium Magnesium Chloride
Urinalysis: (local lab)	pH Leucocytes Erythrocytes Protein Glucose Urobilinogen Ketones Bilirubin Nitrite Specific gravity		

All clinically significant abnormal laboratory values observed at 5 (± 2) days post-dose are to be followed up until they have normalized, or until in the investigator's opinion there is no medical necessity for further blood tests.

